### 1.2 Secondary

The secondary objectives of this study are to:

- Evaluate the pharmacokinetics (PK) of AMG 330
- Determine the formation of anti-AMG 330 antibodies
- Evaluate the anti-leukemia activity of AMG 330 by evaluating
  - the number and proportion of subjects with R/R AML who respond to treatment with AMG 330. Response is defined as any of the following: complete remission (CR), CR with incomplete recovery (CRi), or morphologic leukemia-free state (all according to Revised International Working Group [IWG] response criteria), or CR with partial hematologic recovery (CRh)
  - the number and proportion of subjects with MDS who respond to treatment with AMG 330. Response is defined as any of the following: CR or marrow CR (all according to Revised IWG response criteria)
  - the number and proportion of subjects with MRD-positive AML who respond to treatment with AMG 330. MRD response is defined as conversion from MRD+ with 0.1% threshold to MRD- status
  - the duration of response, time to progression, and time to response.

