### 7.6 Disease Response

For R/R AML (Group 1 and Group 4 in Phase 1a), disease response assessments will be based upon review of cytogenetics, bone marrow aspirates/biopsies, and peripheral blood count. In subjects refusing bone marrow aspirates/biopsies collection after completing treatment, lack of disease response may be documented by the presence of blasts in peripheral blood or in other tissues or fluids (eg, in cerebrospinal fluid collected by lumbar puncture).

Response categories are defined as follows ([Appendix E](#) and Topp et al., 2015):

CR:

- less than 5% blasts in the bone marrow
- absence of blasts with Auer rods
- absence of extramedullary disease
- absolute neutrophil count (ANC)  $\geq 1,000/\mu\text{l}$
- platelet count  $\geq 100,000/\mu\text{l}$
- independence of red cell transfusions

CRi

- all CR criteria except for incomplete recovery of peripheral blood counts (residual neutropenia [ $< 1,000/\mu\text{l}$ ] or thrombocytopenia [ $< 100,000/\mu\text{l}$ ])

Morphologic leukemia-free state

- less than 5% blasts in the bone marrow
- absence of blasts with Auer rods
- absence of extramedullary disease
- no hematologic recovery required

CRh

- less than 5% blasts in the bone marrow
- no evidence of disease
- partial recovery of peripheral blood counts: platelet count  $> 50,000/\mu\text{l}$ , and ANC  $> 500/\mu\text{l}$
- no extramedullary disease

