**Partial Remission (PR)**

- **relevant in the setting of phase I and II clinical trials only**
- **all hematologic criteria of CR**
- **decrease of bone marrow blast percentage to 5% to 25%**
- **decrease of pretreatment bone marrow blast percentage by at least 50%**

Response must be established from a bone marrow sample supplemented with neutrophil and platelet counts.

For R/R AML subjects enrolled in Group 5 (Phase 1a) and all R/R AML Groups in Phase 1b, disease response assessment will be based on ELN recommendations from an international expert panel **and FDA guidance** ([Appendix E](#), Dohner et al, 2017).

Response:

- CR without minimal residual disease (CRMRD-)
- Complete remission (CR)
- **CR with partial hematological recovery (CRh)**
- CR with incomplete **hematological** recovery (CRi)
- Morphologic leukemia-free state (MLFS)
- Partial remission (PR)

Treatment failure:

- Primary refractory disease
- Death in aplasia
- Death from indeterminate cause

Response criteria for clinical trials only:

- Stable disease
- Progressive disease (PD)

Relapse:

- Hematologic relapse (after CRMRD-, CR, CRi)
- Molecular relapse (after CRMRD-)

For MRD+ AML subjects who enroll in Group 2, the conversion from MRD-positive status to MRD negative, is defined as MRD threshold below 0.1% as per ELN recommendations (Schuurhuis et al., 2018). In addition, [REDACTED]

[REDACTED] Response categories are defined as below:

- MRD conversion (MRD positive change to MRD negative)
- No MRD response (MRD remains positive)
- Molecular relapse (previous MRD negative response changes to MRD positive status)

For MDS subjects (Group 3), disease response assessments will be based upon review of cytogenetics ( [Appendix L](#), [Appendix M](#)), bone marrow aspirates/biopsies, and peripheral blood count. Response categories are defined as follows ([Appendix K](#) and Cheson, Blood 2006):

Complete remission

- Bone marrow:  $\leq 5\%$  myeloblasts with normal maturation of all cell lines
- Persistent dysplasia will be noted
- Peripheral blood
  - Hgb  $\geq 11$  g/dL
  - Platelets  $\geq 100 \times 10^9/L$
  - Neutrophils  $\geq 1.0 \times 10^9/L$
  - Blasts 0%

Partial remission

- All CR criteria if abnormal before treatment except:
- Bone marrow blasts decreased by  $\geq 50\%$  over pretreatment but still  $> 5\%$
- Cellularity and morphology not relevant

Marrow CR

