##### **Secondary Endpoints:**

- PK parameters: half-life, steady state concentration, volume of distribution and clearance of AMG 330
- Incidence of anti-AMG 330 antibody formation
- Efficacy parameters for R/R AML: response rate (response defined as CR/CRI/morphologic leukemia-free state [per modified IWG criteria] or CRh), duration of response, time to progression, time to response
- Efficacy parameters for MRD-positive AML: response rate (response defined as conversion from MRD+ status with 0.1% threshold to MRD-), duration of response, time to response
- Efficacy parameters for MDS: response rate (response defined as CR or marrow complete remission [per International Working Group (IWG) standardized response criteria]), duration of response, time to progression, time to response

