2.1 Objectives and Endpoints

Primary Objectives:

- Evaluate the safety and tolerability of AMG 330 in adult subjects with relapsed/refractory AML, MRD+ AML and MDS
- Estimate the maximum tolerated dose (MTD) and/or a biologically active dose [eg, recommended phase 2 dose (RP2D)] of AMG 330 in adult with relapsed/refractory AML, MRD+AML and MDS

Secondary Objectives:

- Evaluate the pharmacokinetics (PK) of AMG 330
- Determine the formation of anti-AMG 330 antibodies
- Evaluate the anti-leukemia activity of AMG 330 by evaluating
 - the number and proportion of subjects who respond to treatment with AMG 330. Response is defined as any of the following: complete remission (CR), CR with incomplete recovery (CRi) or morphologic leukemia-free state (all according to Revised International Working Group [IWG] response criteria) or CR with partial hematologic recovery (CRh).
 - the number and proportion of subjects with MDS who respond to treatment with AMG 330. Response is defined as any of the following: CR or marrow CR (all according to Revised IWG response criteria).
 - the number and proportion of subjects with MRD-positive AML (Group 2) who respond to treatment with AMG 330. Response is defined as conversion from MRD+ status with 0.1% threshold to MRD- status

- the duration of response, event-free survival, time to response, and overall survival

Exploratory Objectives:

- Evaluate the protein, nucleic acid, and cellular biomarkers in blood and / or bone marrow, as applicable [eg, cytokines, lymphocyte subsets, minimal residual disease (MRD – Group 1 only), leukemic stem cells (LSCs)]
- Evaluate effects of genetic variations in and phenotype of cancer genes, including apoptotic markers, on adverse event profile and treatment response
- Evaluate mechanisms of resistance
- Evaluate potential measures of clinical benefit including number of blood products transfused and days of antibiotic treatment of infection
- Evaluate the relationship between AMG 330 exposure and response to treatment
- [REDACTED]
- [REDACTED]
- [REDACTED]
- Explore the additional thresholds of conversions to MRD- status in MRD+ AML subjects as an efficacy measure for AMG 330 treatment

Primary Endpoint:

- Safety: subject incidence and grade of adverse events (AEs) and dose limiting toxicities (DLTs)

Secondary Endpoints:

- Pharmacokinetic parameters: half-life, steady state concentration, volume of distribution and clearance of AMG 330
- Incidence of anti-AMG 330 antibody formation

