- Efficacy parameters for R/R AML: response rate (response defined as CR/CRi/morphologic leukemia-free state [per modified IWG criteria] or CRh), duration of response, time to response, event-free survival and overall survival (duration of response, event-free survival, and overall survival will only be measured in the expansion cohort)
- Efficacy parameters for MRD-positive AML: response rate (response defined as conversion from MRD+ status with 0.1% threshold to MRD-), time to response,

relapse-free survival, and overall survival (relapse-free survival and overall survival will only be measured in the expansion cohort)

- Efficacy parameters for MDS: response rate (response defined as CR or marrow complete remission [per International Working Group (IWG) standardized response criteria]), duration of response, time to response, event-free survival and overall survival (duration of response, event-free survival, and overall survival will only be measured in the expansion cohort)

Exploratory Endpoints:

- Depletion of LSCs
- MRD response
- Lymphocyte counts, cluster of differentiation (CD) 33+ monocytes and T cells, as well as T cell activation (including T cell subsets). Other immune subsets may also be examined
- [REDACTED]
- [REDACTED]
- [REDACTED]
- Changes in serum cytokine levels
- Frequency and severity of cytokine release syndrome (CRS) and other AEs following [REDACTED] premedication, and alternative dose step schedules of AMG330
- [REDACTED]

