5.4 Endpoints

Treatment-Emergent Adverse Event (TEAE)

Events categorized as Adverse Events (AEs) starting on or after first dose of investigational product as determined by "Did event start before first dose of investigational product (enter response based on earliest administration of [REDACTED]
[REDACTED], or AMG330, whichever occurred first)" equal to "No" or missing on the Events eCRF and up to 30 days after last administration of AMG330 or end of study date, whichever is earlier. Disease related events (DREs) will be included in the TEAE summary.

The severity of each adverse event will be graded using the CTCAE version 4.0. Adverse events will be coded using MedDRA. For CRS events, revised grading system will be used as per protocol ([Lee et al. 2014](#)).

Treatment-Related AE

A treatment-related AE is any treatment-emergent AE that per investigator review has a reasonable possibility of being caused by the investigational product.

Dose Limiting Toxicities (DLT)

DLT will be determined by "Is this event a Dose Limiting Toxicity (DLT)?" equal to "Yes" on the Events eCRF. Investigators will determine whether an adverse event qualifies as a DLT per protocol [Section 6.2.1.4](#).

Overall Response:

Overall response definitions are given below for different indications.

Group 1 in dose-escalation cohort / Group 4 (R/R AML)

Response is defined as any of the following:

Complete remission (CR), CR with incomplete recovery (CRI) or morphologic leukemia-free state (MLFS) (all according to Revised International Working Group [IWG] response criteria for AML), or CR with partial hematologic recovery (CRh).

Group 2 (MRD+ AML) (Primary)

Response is defined as CR without minimal residual disease (CRMRD-) or CRI without minimal residual disease (CRiMRD-). MRD- is defined as MRD threshold below 0.1% as per ELN recommendations ([Schuurhuis et al., 2018](#)).

Group 2 (MRD+ AML) (Exploratory)

Group 3 (MDS)

Response is defined as any of the following:

CR or marrow CR (all according to Revised IWG response criteria for MDS)

Group 5 and Group 1 in dose-expansion cohort (R/R AML)

Response is defined as any of the following: CRMRD-, CR, CRi, CRh, MLFS, PR.

Minimum Residual Disease (MRD) Response (All groups):

Minimum residual disease response is defined as MRD negative, indicating presence of leukemia cells to 0.1% or lower of white blood cells.

Duration of Response (DOR):

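### The R/R AML response endpoint excludes partial remission, but SAP 5.4 counts it for the Group 1 expansion cohort and Group 5, and the response rate is calculated from SAP 5.4

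*SAP*

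**What the plan says.** **Without PR.**

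- Protocol 1.2, secondary objective: "Response is defined as any of the following: complete remission (CR), CR with incomplete recovery (CRi), or morphologic leukemia-free state", with CRh added after it.
- SAP 2.1, secondary objective, has the same list: "Response is defined as any of the following: complete remission (CR), CR with incomplete recovery (CRi) or morphologic leukemia-free state", again followed by CRh.
- Protocol 10.1.1, secondary endpoint: "Efficacy parameters for R/R AML: response rate (response defined as CR/CRI/morphologic leukemia-free state [per modified IWG criteria] or CRh".
- SAP 2.1, secondary endpoint: "Efficacy parameters for R/R AML: response rate (response defined as CR/CRi/morphologic leukemia-free state [per modified IWG criteria] or CRh". The same bullet goes on to name the expansion cohort, as the only place where duration of response, event-free survival (EFS) and overall survival are measured. It gives that cohort no separate response definition.
- Protocol 3.1.1 defines a responding subject for continuing Group 1 expansion past the first 10 subjects by the same four categories.

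**With PR.**

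- SAP 5.4, Overall Response, Group 5 and Group 1 expansion: "Response is defined as any of the following: CRMRD-, CR, CRi, CRh, MLFS, PR".
- Protocol 7.6 introduces a list based on ELN and FDA criteria with "For R/R AML subjects enrolled in Group 5 (Phase 1a) and all R/R AML Groups in Phase 1b". PR is one of six categories under its response heading.

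**Listed but not counted.** Protocol 7.6 has a separate set of categories introduced by "For R/R AML (Group 1 and Group 4 in Phase 1a), disease response assessments will be based upon review of cytogenetics". PR is in that set too, described as "relevant in the setting of phase I and II clinical trials only". SAP 5.4 does not count PR for Group 1 escalation or Group 4.

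**What uses the definition.** SAP 9.5.2 calculates the proportion responding, with exact 80% and 95% intervals, from the definition in SAP 5.4. Time to response (TTR), duration of response (DOR) and EFS in SAP 5.4 also depend on who is a responder.

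**The concern.** A programmer who follows SAP 9.5.2 and 5.4 will produce a Group 1 expansion response rate that includes PR. A reader who takes the endpoint from SAP 2.1 or Protocol 10.1.1 will assume that it does not. Both would call the result the secondary endpoint.

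The same word would also carry two meanings within Group 1: no PR in escalation, PR in expansion. Protocol 10.4.3.2 tabulates response for subjects treated at the MTD, and that set can draw on both phases.

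Responder status also determines EFS. SAP 5.4 dates the event of every non-responder at the first dose, so the classification of a PR-only subject decides whether that subject has an event at once or is followed further.

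**Working it through.** **1. The plan's own figures.** SAP 3.2 and Protocol 10.2 give the chance of stopping expansion, that is, of no responder among 10 subjects:

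- P(stop) = (1 − p)^10
- p = 5%: 0.95^10 = 0.599 (plan: greater than 59% for a rate below 5%)
- p = 20%: 0.80^10 = 0.107 (plan: less than 11% for a rate above 20%)

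These are correct for a given response rate under either definition.

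The exact (Clopper-Pearson) interval for x responders out of n, with α = 1 − confidence level, is:

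- lower limit = α/2 quantile of Beta(x, n − x + 1)
- upper limit = 1 − α/2 quantile of Beta(x + 1, n − x)

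At 80% this gives 5.5% to 45.0% for 2/10 and 10.9% to 32.5% for 6/30, as in the plan.

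**2. The two definitions side by side.**

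| Category | Objective, endpoint, Protocol 3.1.1 | SAP 5.4, Group 1 expansion and Group 5 |
|---|---|---|
| CR (with or without MRD) | yes | yes |
| CRi | yes | yes |
| CRh | yes | yes |
| MLFS | yes | yes |
| PR | no | yes |

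CR without MRD is already a CR, so PR is the only real difference. Every responder under the endpoint is a responder under SAP 5.4. The SAP 5.4 rate is therefore equal or higher, never lower.

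**3. Size.** The documents give no PR rate, so one to three PR-only subjects are assumed, added to the plan's own 20% case. Each adds 1/30 = 3.3 points.

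| Responders | Rate | 80% CI | 95% CI |
|---|---|---|---|
| 6/30 (no PR-only) | 20.0% | 10.9 to 32.5 | 7.7 to 38.6 |
| 7/30 (one PR-only) | 23.3% | 13.5 to 36.1 | 9.9 to 42.3 |
| 8/30 (two) | 26.7% | 16.2 to 39.7 | 12.3 to 45.9 |
| 9/30 (three) | 30.0% | 19.0 to 43.2 | 14.7 to 49.4 |

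If the cohort ends at 10, one PR-only subject moves 2/10 = 20% (80% CI 5.5 to 45.0) to 3/10 = 30% (11.6 to 55.2).

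**4. EFS for a PR-only subject.** The SAP 5.4 events are treatment failure, relapse in a responder, and death. Progression is not one of them, although it does end DOR.

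- If PR counts as response, a PR subject who progresses has no clearly defined EFS event.
- If PR does not count, the non-responder rule puts the event at first dose. Appendix E of the protocol, in its phase I wording for resistant disease, does not treat a PR as failure.

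The plan settles neither case.

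**The case against.** **SAP 5.4 follows the protocol.** For exactly these subjects Protocol 7.6 prescribes ELN- and FDA-based assessment and puts the same six categories under response. A reader might infer from SAP Section 10, which does not mention PR, that the SAP introduced PR as an undeclared departure from the protocol. The documents do not support that: the conflict is already present between Protocol 7.6 and Protocol 1.2, 3.1.1 and 10.1.1. The objection explains where PR came from. It does not remove the inconsistency, because the endpoint text makes no exception for these groups. Nor does a place in Protocol 7.6 settle endpoint status, since PR is also among the categories there for Group 1 escalation and Group 4, where SAP 5.4 leaves it out. It is fair to add that the later list is set out differently and puts PR expressly under a response heading.

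**The continuation rule is already defined.** A reader might infer that a single PR among the first 10 would keep Group 1 expansion open. The SAP text (3.1 and 7.1) leaves the responding subject undefined, but Protocol 3.1.1 defines it without PR and nothing in the SAP overrides that. Continuation also needs review by the Dose Level Review Team. What remains is a missing cross-reference.

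**Relapse after CRh or MLFS.** The relapse wordings in Protocol 7.6 and Appendix E differ, and a reader might infer that such a relapse may not be an EFS event. SAP 5.4 counts relapse for responders, which include both categories, and Protocol 6.2.1.5 speaks of relapse after all four. That reading does not hold.

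**Size and direction.** The PR-only counts are assumed, and the shifted estimates of 23.3% to 30.0% all lie within the plan's own 80% interval. Phase I trials can reasonably count PR or not. Both points stand. For Group 5, with 6 to 12 subjects, further analysis is deferred to a supplementary plan that is not among the documents, so no size is claimed there.

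**Conclusion.** The R/R AML response definition is inconsistent, and the plan is wrong as written on this point. Followed literally, SAP 9.5.2 and 5.4 report a Group 1 expansion response rate that is not the secondary endpoint stated in SAP 2.1 and Protocol 10.1.1, and that differs from the definition used for Group 1 escalation. The direction is certain: equal or higher. The amount is 3.3 points per PR-only subject at n = 30 and 10 points at n = 10, and the number of such subjects is an assumption.

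The 59% and 11% stopping figures are arithmetically right, and Protocol 3.1.1 governs continuation for Group 1. Protocol 10.4.3.2 calls the efficacy analyses exploratory, so the effect is on how the result is read and on comparability between phases. No formal test is affected. The one EFS gap is the PR-only subject. This should be fixed before the expansion data are analysed.

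**What to change.** Use one definition throughout. Either choice is defensible.

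**(a) PR does not count.** In SAP 5.4, base the response rate, TTR and DOR for Group 1 expansion and Group 5 on the stated endpoint: CR with or without MRD, CRh, CRi, MLFS. Tabulate PR as its own category, with a labelled supplementary row for response including PR. State in Protocol 7.6 that PR is an assessment category. For EFS, say whether the non-responder rule dates a PR-only subject's event at first dose, given that Appendix E's phase I wording does not class PR as failure.

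**(b) PR counts.** Amend Protocol 1.2, 3.1.1 and 10.1.1 and SAP 2.1 to say so for these groups. List the change in SAP Section 10. State that the 5% and 20% rates behind the stopping figures include PR. Add progression as an EFS event for PR responders.

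**Under either choice**, cite the chosen responder definition where SAP 3.1 and 7.1 describe continuation of expansion.

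**Cost.** Option (a) needs SAP wording, one table row and one sentence in Protocol 7.6, and the headline expansion rate may be lower than under the present SAP 5.4. Option (b) needs changes to three protocol sections and to the SAP. SAP Section 10 already anticipates a Protocol Amendment 10, which could carry the protocol wording. Neither option needs new data.

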**Table 24. List of Analytes**

Chemistry	Hematology	Urinalysis	Coagulation	Other Labs
Sodium	Erythrocytes	Specific gravity	PT	Pregnancy test a
Potassium	Hemoglobin	pH	PTT	Serology (HepB, HepC)
Bicarbonate	Hematocrit	Blood	INR	
Or	MCV	Protein	Fibrinogen	MRD (for subjects with <5% blasts in bone marrow; Groups 1 and 2)
Total CO 2	Platelets	Glucose	AT III	
Chloride	WBC Differential	Bilirubin		
Total protein	Total Neutrophils	Ketones		
Albumin	Seg. Neutrophils	Microscopic exam		
Adjusted	Lymphocytes	(performed at the discretion of the investigator)		
Calcium	Atypical Lymphocytes			
Magnesium	Monocytes			
Phosphorus	Bands/Stabs			
Glucose	Eosinophils			
Creatinine	Basophils			
Total bilirubin	Blasts			
ALP	Myeloblasts			
AST	Monoblasts			
ALT	Megakaryoblasts			
GGT	Promyelocytes			
Amylase	Myelocytes			
Lipase	Metamyelocytes			
CRP	Nucleated RBC			
LDH	Immature			
Uric Acid	Granulocytes			
Ferritin				

ALP = alkaline phosphatase; ALT = alanine aminotransferase; anti-HBc = Hepatitis B core antibody; AST = aspartate aminotransferase; AT III = Antithrombin III; CRP = C-reactive protein; **GGT = gamma-glutamyl transferase**; HepBsAg = hepatitis B surface antigen; HepCAB = hepatitis C antibody; INR = international normalize ratio; LDH = lactate dehydrogenase; MCV = mean corpuscular volume; PT = prothrombin time; PTT = partial thromboplastin time; WBC = white blood cell

a Serum pregnancy test will be performed for all females unless surgically sterile or ≥ 2 years postmenopausal.

Additional procedures (eg collection of an unscheduled blood sample to measure cytokine levels) deemed necessary as part of standard of care or as required by local laws and regulations may be performed at the investigator's discretion.

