#### **7.5.2.1 MRD Testing for Screening/Eligibility for Subjects in Group 2**

For subjects to be eligible for study participation in Group 2, bone marrow aspirate is required prior to enrollment to establish MRD status. Collection of bone marrow aspirate following local standard of care procedure for MRD testing is not expected to present any additional risk to the health, safety, and welfare of the subject. Screening for MRD will be conducted using an investigational diagnostic or validated local test/assay with a minimum  $10^{-3}$  sensitivity at a CLIA certified laboratory (for US only) agreed upon by the Sponsor as listed in [Table 15](#) (Section 7.3.9); local testing is sufficient for the enrollment decision, if the test result is from < 21 days from the start of treatment. Additional bone marrow aspirate from the first bone marrow pull is required to be sent for testing at central lab and retrospective analysis for all subjects enrolled in Group 2. Timing of sample collection is described in the Schedule of Activities.

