8.3 Handling of Missing and Incomplete Data

The following imputation for missing or incomplete data will be performed if required: Incomplete adverse event and concomitant medication dates missing data will be imputed as described in [Appendix A](#).

Non-pharmacokinetic measurements (eg, biomarker data) that are below the lower limit of quantification will be considered equal to half of the lower limit of quantification for all analyses unless specified otherwise.

- Laboratory measurements that are below the quantification limits will be considered equal to the lower limit of quantification for all analyses unless explicitly noted otherwise.
- Biomarker data that are below the quantification limits will be considered equal to half of the lower limit of quantification for all analyses unless specified otherwise.
- PD concentrations that are below the quantification limits will be set to zero when engaging non-compartmental model to compute PD parameters.

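### MRD negativity is below 0.1% for Group 2 response but 0.1% or lower for MRD response, so a result of exactly 0.1% is classified both ways

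*SAP*

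**What the plan says.** SAP 5.4 defines Group 2 overall response as CR or CRi without MRD and adds: "MRD- is defined as MRD threshold below 0.1% as per ELN recommendations". Protocol 7.6 uses the same strict cut-off for conversion in Group 2, which "is defined as MRD threshold below 0.1% as per ELN recommendations". Further down SAP 5.4, under a heading that covers all groups: "Minimum residual disease response is defined as MRD negative, indicating presence of leukemia cells to 0.1% or lower of white blood cells". SAP 9.5.2 reports both quantities: overall response by cohort, and MRD response at 0.1% and at 0.01% in the Safety Analysis Set.

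On results below the assay limit, SAP 8.3 has two rules. One reads: "Laboratory measurements that are below the quantification limits will be considered equal to the lower limit of quantification for all analyses". The other reads: "Biomarker data that are below the quantification limits will be considered equal to half of the lower limit of quantification". Neither names MRD. The protocol lists MRD among the clinical laboratory analytes (Table 24) and treats it as a biomarker (Section 7.5).

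The readable text states no limit of quantification (LLOQ) for MRD. It gives two related figures. Protocol 7.5.2.1 asks that Group 2 screening use an "investigational diagnostic or validated local test/assay with a minimum" sensitivity of 10^-3. Protocol 7.5.2 puts the detection ability of the flow method at about 1 in 1,000 to 1 in 10,000.

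**The concern.** One label, MRD-negative, carries two inequalities in the same SAP section. A programmer who follows each definition as written would code a 0.1% result as a failure to convert in the Group 2 response table and as a success in the MRD response table. A reader of the two tables could not tell whether a difference between them came from the CR/CRi requirement, which is intended, or from the cut-off, which looks accidental.

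The below-limit rules raise a related question. An undetectable result is the clearest evidence of conversion. If such a result were replaced by a number that sits on the cut-off, the choice of inequality would no longer be a matter of rare ties.

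**Working it through.** There is no plan figure to reproduce here, since the point concerns classification and not sample size or power.

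**Step 1. A measured result of exactly 0.1%.** Group 2 cut-off: 0.1 < 0.1 is false, so MRD-positive. MRD response cut-off: 0.1 ≤ 0.1 is true, so a response. No assumption is needed.

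**Step 2. The scale.** 10^-3 = 0.1%. One in 1,000 = 0.1%, and one in 10,000 = 0.01%. The least sensitive end of the quoted range therefore equals the cut-off, and the most sensitive end is ten times lower.

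**Step 3. A below-limit sample, if its status were computed from the imputed value.** The LLOQ is assumed across that range. The laboratory rule gives LLOQ and the biomarker rule gives LLOQ/2.

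| Assumed LLOQ | Rule | Imputed value | Below 0.1% (Group 2) | 0.1% or lower (MRD response) |
|---|---|---|---|---|
| 0.1% | laboratory | 0.1% | no | yes |
| 0.1% | biomarker | 0.05% | yes | yes |
| 0.05% | laboratory | 0.05% | yes | yes |
| 0.05% | biomarker | 0.025% | yes | yes |
| 0.02% | laboratory | 0.02% | yes | yes |
| 0.02% | biomarker | 0.01% | yes | yes |
| 0.01% | laboratory | 0.01% | yes | yes |
| 0.01% | biomarker | 0.005% | yes | yes |

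Only one of the eight rows conflicts: LLOQ 0.1% with the laboratory rule.

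**Step 4. Would aligning the inequality be enough?** In that one row, a common cut-off of below 0.1% makes the two endpoints agree, but they agree that an undetectable sample is MRD-positive. So the inequality and the below-limit convention are separate repairs.

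**Step 5. The 0.01% summary.** With an LLOQ of 0.1% the imputed values (0.1% and 0.05%) both exceed 0.01%, so such an assay cannot inform that threshold. With an LLOQ of 0.02% the biomarker rule imputes exactly 0.01%, which passes an inclusive cut-off and fails a strict one, although the assay cannot resolve that level. Any below-limit convention should therefore compare the sample's assay limit with each threshold.

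**The case against.** The strongest reply is that the mismatch is one phrase and exact ties should be few. Efficacy is not primary (SAP 9.5.1), and Protocol 10.4.3.2 calls the efficacy analyses exploratory. The two endpoints also differ by design, because Group 2 response requires CR or CRi and MRD response does not. All of this is fair and limits the size of the point. It does not explain why the same status has two cut-offs.

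A reader might infer something stronger: that the below-limit rules place undetectable results at 0.1%, so that true converters are counted as Group 2 non-responders. The documents do not support that, for these reasons:

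- It needs an LLOQ of 0.1%. The 10^-3 figure is a minimum sensitivity for the screening assay, not an LLOQ. On-treatment MRD samples go to a central laboratory (Protocol 7.5.2.2 and 7.7). A footnote to Protocol Table 12 does require local as well as central MRD testing in Group 2, but a minimum sensitivity is still not an LLOQ.
- The 0.01% summary in SAP 9.5.2 suggests an assay that resolves well below 0.1%.
- The biomarker reading is the more natural one for MRD, and it gives no conflict at 0.1%.
- Nothing says that status is computed from an imputed number. Protocol 7.5.2 has a hematopathologist determine MRD, and the Group 2 response categories in Protocol 7.6 are positive or negative.
- Text is blacked out near the MRD method and threshold passages in Protocol 7.5.2 and 7.6, so an LLOQ not visible here cannot be called missing.

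It is also tempting to say that one such subject would decide whether a Group 2 expansion cohort continues past its first 10 subjects. That does not follow either. Continuation is a Dose Level Review Team judgement on all available data, and Protocol 3.1.5 says only that further subjects may be enrolled.

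**Conclusion.** The contradiction in SAP 5.4 stands without assumptions: a result of exactly 0.1% is MRD-positive for Group 2 response and an MRD response in the SAP 9.5.2 summary. Its certain reach is limited to such results. How many there will be depends on the precision with which MRD is reported, which the readable text does not give.

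The below-limit point is secondary. What stands is that SAP 8.3 does not assign MRD to either rule, and that MRD could fall under both. Misclassification of below-limit samples at 0.1% would require an LLOQ of 0.1%, the laboratory rule, and status derived from the imputed value, all together. None of these is stated, so no number of affected subjects should be attached to it.

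**What to change.** In SAP 5.4, reword the MRD response definition as: *MRD negative, defined as leukemia cells below 0.1% of white blood cells*. This matches the Group 2 cut-off and Protocol 7.6.

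In SAP 8.3, add: *MRD status is not derived from imputed values; a result below the assay limit is MRD-negative at a given threshold (0.1% or 0.01%) only if that sample's assay limit is at or below the threshold.* The condition on the assay limit matters. Without it, a poor sample with a limit above 0.1% would count as negative at 0.1%, and an assay with a limit of 0.1% would count towards the 0.01% summary.

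The cost is two SAP sentences. Neither changes the samples collected or the conduct of the trial, but the second needs the assay limit of each below-limit result to be available to the analysis.
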